10.3.2 Reporting of serious adverse events

All SAEs will be reported, whether or not considered causally related to the investigational product, or to the study procedure(s). The reporting period for SAEs is the period immediately following the time that written informed consent is obtained through 90 days after the last dose of durvalumab + tremelimumab or until the initiation of alternative anticancer therapy. The investigator and/or Sponsor are responsible for informing the Ethics Committee and/or the Regulatory Authority of the SAE as per local requirements.

NOTE TO AUTHOR: For trials conducted in the United States, the following must be included (similar language must be included, referencing the appropriate health authority and reporting mechanism, for studies conducted outside of the United States). Note that all serious or unexpected adverse events must be reported to AstraZeneca regardless of the country where the study is conducted:

The investigator and/or sponsor must inform the FDA, via a MedWatch/AdEERs form, of any serious or unexpected adverse events that occur in accordance with the reporting obligations of 21 CFR 312.32, and will concurrently forward all such reports to AstraZeneca. A copy of the MedWatch/AdEERs report must be faxed to AstraZeneca at the time the event is reported to the FDA. It is the responsibility of the sponsor to compile all necessary information and ensure that the FDA receives a report according to the FDA reporting requirement timelines and to ensure that these reports are also submitted to AstraZeneca at the same time.

* A **cover page** should accompany the **MedWatch/AdEERs** form indicating the following:

- “Notification from an Investigator Sponsored Study”

- The investigator IND number assigned by the FDA
- The investigator's name and address
 - The trial name/title and AstraZeneca ISS reference number (ESR-16-11857)

* Sponsor must also indicate, either in the SAE report or the cover page, the ***causality*** of events ***in relation to all study medications*** and if the SAE is ***related to disease progression***, as determined by the principal investigator.

**** Send SAE report and accompanying cover page by way of email to AstraZeneca's designated mailbox:*** [contact]

If a non-serious AE becomes serious, this and other relevant follow-up information must also be provided to AstraZeneca and the FDA.

Serious adverse events that do not require expedited reporting to the FDA still need to be reported to AstraZeneca preferably using the MedDRA coding language for serious adverse events. This information should be reported on a monthly basis and under no circumstance less frequently than quarterly.

10.3.2.1 Reporting of deaths

All deaths that occur during the study, or within the protocol-defined 90-day post-last dose of durvalumab + tremelimumab safety follow-up period must be reported as follows:

- Death that is clearly the result of disease progression should be documented but should not be reported as an SAE.
- Where death is not due (or not clearly due) to progression of the disease under study, the AE causing the death must be reported to as a SAE within **24 hours** (see Section 10.3.2 for further details). The report should contain a comment regarding the co-involvement of progression of disease, if appropriate, and should assign main and contributory causes of death.
- Deaths with an unknown cause should always be reported as a SAE.

Deaths that occur following the protocol-defined 90-day post-last-dose of durvalumab safety follow-up period will be documented as events for survival analysis, but will not be reported as an SAE.

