1.1.5 Radiation therapy

Uncontrolled loco regional disease is a major concern in head and neck cancer as it severely compromises a patient's quality of life with pain, ulceration, bleeding, foul odor, speech, swallowing, and breathing difficulties etc. Historically, radiation therapy has underpinned any and all attempts at providing durable disease control in the head and neck region.

In this protocol, palliative radiation therapy will be administered using either hypofractionated Image guided Radiotherapy (HIGRT) or Stereotactic ablative body radiotherapy (SBRT). These two techniques involve precise delivery of large tumoricidal/ablative doses of radiation treatments to a small tumor over 1-5 fractions using image guidance and elaborate treatment planning process aimed at providing steep dose gradients especially near critical organs. Distinct nontraditional radiobiological mechanisms may be involved with the high dose fractions ($>/= 6$ Gy) used with HIGRT/SBRT, as compared with conventionally fractionated (1.8-2 Gy) radiotherapy that is commonly used in the curative setting. HIGRT/SBRT may produce biological effects mediated through enhanced immune stimulation and endothelial damage of the tumor micro environment. (Karam et al. Future Oncol. 2015). As a primary modality for medically unfit patients, SBRT has offered reasonable local control with acceptable toxicity. In the re-irradiation setting, SBRT is associated with higher rates of morbidity (10-50%) and even mortality (1-5%) in the face of promising local control.

There is now increasing data on the feasibility of hypofractionated radiation administered concurrent with immune checkpoint inhibition. Recent publication of the randomized phase 2 SABR-COMET study (Palma et al. Lancet 2019) (SBRT) in the oligometastatic setting significantly improves overall survival and progression free survival compared to palliative standard of care. This trial targeted all known metastatic lesions and was not in combination

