10.3.1 Study recording period and follow-up for adverse events and serious adverse events

Adverse events and serious adverse events will be recorded from time of administration of the first dose of investigational drug, throughout the treatment period and including the follow-up period (90 days after the last dose of durvalumab + tremelimumab).

During the course of the study all AEs and SAEs should be proactively followed up for each subject. Every effort should be made to obtain a resolution for all events, even if the events continue after discontinuation/study completion.

If a subject discontinues from treatment for reasons other than disease progression, and therefore continues to have tumor assessments, drug or procedure-related SAEs must be captured until the patient is considered to have confirmed PD and will have no further tumor assessments.

The investigator is responsible for following all SAEs until resolution, until the subject returns to baseline status, or until the condition has stabilized with the expectation that it will remain chronic, even if this extends beyond study participation.

Follow-up of unresolved adverse events

Any AEs that are unresolved at the subject's last visit in the study are followed up by the investigator for as long as medically indicated, but without further recording in the CRF. After 90 days, only subjects with ongoing investigational product-related SAEs will continue to be followed for safety.

AstraZeneca/MedImmune retains the right to request additional information for any subject with ongoing AE(s)/SAE(s) at the end of the study, if judged necessary.

Post study events

After the subject has been permanently withdrawn from the study, there is no obligation for the investigator to actively report information on new AE or SAEs occurring in former study subjects after the 90-day safety follow-up period for patients treated with durvalumab + tremelimumab. However, if an investigator learns of any SAEs, including death, at any time after the subject has been permanently withdrawn from study, and he/she considers there is a reasonable possibility that the event is related to study treatment, the investigator should notify the study sponsor and AstraZeneca/MedImmune Drug Safety.

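### Sections 10.3.1 and 10.3.2.1 give opposite instructions for a treatment-related death more than 90 days after the last dose, so its attribution and Grade 5 status may be missing from the safety summary

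*Combined protocol and SAP*

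**What the plan says.** The last sentence of Section 10.3.2.1 covers all deaths after the 90-day safety follow-up period. They "will be documented as events for survival analysis, but will not be reported as an SAE". It makes no distinction by cause.

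Section 10.3.1 has two provisions that reach beyond 90 days for related events:

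- For subjects who stop treatment for a reason other than progression and continue tumor assessments, "drug or procedure-related SAEs must be captured until the patient is considered to have confirmed PD". No 90-day limit is attached.
- For former subjects, "there is no obligation for the investigator to actively report information on new AE or SAEs" after the 90-day period. However, "if an investigator learns of any SAEs, including death, at any time after the subject has been permanently withdrawn from study" and sees a reasonable possibility that it is related to study treatment, "the investigator should notify the study sponsor and AstraZeneca/MedImmune Drug Safety".

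Other places side with a 90-day limit. Section 10.3.2 sets the SAE reporting period to run "through 90 days after the last dose of durvalumab + tremelimumab or until the initiation of alternative anticancer therapy". Appendices 2 and 3 schedule AE/SAE assessment only at day 30 and months 2 and 3.

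Section 11.2.1 makes safety and tolerability the primary endpoint, assessed in all enrolled patients, and states no time limit.

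**The concern.** A death caused by study drug or study radiation is the most serious outcome that the primary endpoint can contain. Patients are followed for survival until the study ends (Section 8.1.3), so such a death is likely to become known. The question is whether it is recorded as a toxicity or only as a survival event.

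Radiation makes this more than a formality. Section 1.1.5 cites mortality of 1-5% for SBRT in the re-irradiation setting, and Section 4.1 admits previously irradiated sites after a 6-month interval. The safety window is counted from the last drug dose, whereas radiation begins two weeks after the first. In a patient who receives only one dose, the window therefore closes fairly soon after radiation.

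**Working it through.** **1. One case under both rules.** Take a patient who stops for toxicity, has no confirmed progression, continues tumor assessments, and dies on day 120 after the last dose of an event judged possibly related to treatment.

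- Section 10.3.2.1: a survival event, not an SAE.
- Section 10.3.1, first provision: if the event is drug- or procedure-related, it must be captured as an SAE.
- Section 10.3.1, second provision: if the patient has been permanently withdrawn and the investigator learns of the death, it should be notified.

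Neither section refers to the other or says which prevails. There is a similar tension inside 10.3.2.1. Its opening sentence also applies SAE reporting to deaths during the study, and Section 13.3 ends the study at the last patient's last visit.

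**2. What depends on SAE status.** Section 10.3 lists the variables for every AE, with causality rated only against durvalumab or tremelimumab. Date of death with probable cause, and causality in relation to the study radiation, are on the additional list for SAEs. Section 9.1 records death for PFS and OS, and Appendices 2 and 3 record survival status. None of these asks for cause. If 10.3.2.1 is followed, the protocol names no field in which a late death could be attributed to radiation.

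**3. The plan's own figures (Section 11.3).**

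- Half-width at n = 20: 1.96 × √(0.5 × 0.5 / 20) = 0.219. The stated 22% reproduces.
- Chance of seeing a toxicity of 10% prevalence: 1 − 0.9^20 = 0.878. The stated figure of at least 87% reproduces.

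Neither figure changes under the point made here.

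**4. Size of one uncounted death.** Exact (Clopper-Pearson) 95% limits at n = 20, assuming exactly one related death after the window:

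- Counted: 1/20 = 5.0%. The lower limit is 1 − 0.975^(1/20) = 0.1%. The upper limit, the 0.975 quantile of Beta(2, 19), is 24.9%.
- Not counted: 0/20 = 0%. The upper limit is 1 − 0.025^(1/20) = 16.8%.

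The fatal-toxicity rate moves by 5 points and its upper limit by about 8 (24.9 − 16.8 = 8.1). Section 11.3 uses the upper confidence bound as its yardstick for a clinically significant increase in toxicity.

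**5. Decision rules.** DLTs are assessed in the run-in over 28 days (Section 6.4) or 8 weeks (Section 3.3) from the start of treatment. The Grade 4+ rule in Section 3.3 runs to 30 days after the last infusion. A death more than 90 days after the last dose lies outside all of these.

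**6. The anchor.** Section 10.3.2.1 counts the 90 days once from the last dose of both drugs together and once from the last dose of durvalumab. On the planned Q4W schedule:

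- The fourth tremelimumab dose falls on day 1 + 3 × 28 = 85.
- The thirteenth durvalumab dose falls on day 1 + 12 × 28 = 337.
- These are 252 days, or 36 weeks, apart. The window would close on day 175 or day 427 depending on the anchor.

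Radiation starts on about day 15. The window then closes 427 − 15 = 412 days (about 59 weeks) after radiation starts in a patient who completes durvalumab, but 91 − 15 = 76 days after in a patient who receives one dose only.

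**The case against.** The strongest reply is that 10.3.2.1 is a reporting rule and not an analysis rule. Section 11.2.1 covers all enrolled patients with no cut-off date. The 90-day sentence agrees with the general recording period, with Section 10.3.2 and with the appendices, and 10.3.1 can be read as the specific exception for related events. On that reading nothing is lost. This stands in part: a reader might infer that a late toxic death necessarily drops out of the safety result, and the documents do not support that. It drops out only if 10.3.2.1 prevails.

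Three further limits also stand.

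- An SAE that began inside the window is already in the data, and Section 10.3.1 requires SAEs to be followed to resolution or stabilization. What may be lost is its fatal outcome, because AEs unresolved at the last visit are followed without further CRF recording.
- Only the capture provision is mandatory. The notification provision is advisory, depends on the investigator learning of the event, and does not say that the event enters the study database.
- Section 10.3 lists study procedures and radiation as separate causality items, so it is unclear whether the capture provision covers a purely radiation-related death. This weakens the contradiction for such a death but leaves its recording just as uncertain.

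Two other inferences should be resisted. One is that the Grade 4+ stopping count is distorted; its window closes at 30 days. The other is to turn the cited 1-5% mortality into a probability of losing a death. The documents give neither the number of re-irradiated patients nor the share of such deaths after the window. Section 4.2 also excludes previously irradiated lesions with carotid encasement, an unprotected carotid or skin infiltration.

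**Conclusion.** The contradiction holds. For a treatment-related death more than 90 days after the last dose, 10.3.2.1 gives one instruction and 10.3.1 another, and nothing in the protocol settles which applies. If 10.3.2.1 is followed, the death remains in OS, but its attribution and Grade 5 status may be absent from the primary safety summary. The illustration of 5 points on the rate and about 8 on the upper limit assumes one such death among 20 patients. It is not a forecast that one will occur. The sample size, its stated precision, the DLT decision and the stopping rule are all unchanged. The point is worth correcting because it concerns the primary endpoint and the correction is small.

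**What to change.** Make three changes by amendment.

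1. Make the last sentence of 10.3.2.1 expressly subject to the provisions of 10.3.1 for related events, so that the two sections no longer conflict.
2. State in Section 11.2.1 that deaths after the 90-day window judged possibly related to study drug or study radiation are included in the toxicity summary as Grade 5.
3. Define the 90-day window from one named last dose and use that anchor throughout 10.3.2.1.

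The text change is a few sentences. The running cost is an occasional extra SAE report and an entry for cause and relatedness when a death is found in survival follow-up, because cause is not shown as collected there now. No dose, schedule or treatment rule is touched.

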10.3.3 Other events requiring reporting

10.3.3.1 Overdose

An overdose is defined as a subject receiving a dose of durvalumab + tremelimumab in excess of that specified in the Investigator's Brochure, unless otherwise specified in this protocol.

Any overdose of a study subject with durvalumab + tremelimumab, with or without associated AEs/SAEs, is required to be reported within 24 hours of knowledge of the event to the sponsor and AstraZeneca/MedImmune Patient Safety or designee using the designated Safety e-mailbox (see Section 10.3.2 for contact information). If the overdose results in an AE, the AE must also be recorded as an AE (see Section 10.3). Overdose does not automatically make an AE serious, but if the consequences of the overdose are serious, for example death or hospitalization, the event is serious and must be recorded and reported as an SAE (see Section 10.3 and Section 10.3.2). There is currently no specific treatment in the event of an overdose of durvalumab or tremelimumab.

The investigator will use clinical judgment to treat any overdose.

10.3.3.2 Hepatic function abnormality

Hepatic function abnormality (as defined in Section 10.1.3.) in a study subject, with or without associated clinical manifestations, is required to be reported as "hepatic function abnormal" ***within 24 hours of knowledge of the event*** to the sponsor and AstraZeneca/MedImmune Patient Safety using the designated Safety e-mailbox (see Section 10.3.2 for contact information), unless a definitive underlying diagnosis for the abnormality (e.g., cholelithiasis or bile duct obstruction) that is unrelated to investigational product has been confirmed.

- If the definitive underlying diagnosis for the abnormality has been established and is unrelated to investigational product, the decision to continue dosing of the study subject will be based on the clinical judgment of the investigator.
- If no definitive underlying diagnosis for the abnormality is established, dosing of the study subject must be interrupted immediately. Follow-up investigations and inquiries must be initiated by the investigational site without delay.

Each reported event of hepatic function abnormality will be followed by the investigator and evaluated by the sponsor and AstraZeneca/MedImmune.

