 - Grade 3 or 4 neutropenia that is not associated with fever or systemic infection that improves by at least 1 grade within 3 days. Grade 3 or Grade 4 febrile neutropenia will be a DLT regardless of duration or reversibility

- Grade 3 or 4 lymphopenia
- Grade 3 thrombocytopenia that is not associated with clinically significant bleeding that requires medical intervention, and improves by at least 1 grade within 3 days
- Isolated Grade 3 electrolyte abnormalities that are not associated with clinical signs or symptoms and are reversed with appropriate maximal medical intervention within 3 days
- Prolonged delay (>2 weeks) in initiating cycle 2 due to treatment-related toxicity
- Grade 5 toxicity, i.e. death

Dose modification/delays according to Section 6.5.1 and Appendix 1 will apply to the patients who experience DLTs in the run in phase.

Immune-related AEs are defined as AEs of an immune nature (ie, inflammatory) in the absence of a clear alternative etiology. In the absence of a clinically significant abnormality, repeat laboratory testing will be conducted to confirm significant laboratory findings prior to designation as a DLT.

6. 5 Dose Modification and Toxicity Management

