AEs of pneumonitis are also of interest for AstraZeneca, as pneumonitis has been observed with use of anti-PD-1 mAbs (but not with anti-PD-L1 mAbs). Initial work-up should include a high-resolution CT scan, ruling out infection, and pulse oximetry. Pulmonary consultation is highly recommended. Guidelines for the management of patients with immune-related AEs (irAEs) including pneumonitis are provided in Appendix 1.

Infusion reactions

AEs of infusion reactions (also termed infusion-related reactions) are of special interest to AstraZeneca and are defined, for the purpose of this protocol, as all AEs occurring from the start of IP infusion up to 48 hours after the infusion start time. For all infusion reactions, SAEs should be reported to AstraZeneca Patient safety as described in Section 10.3.

Hypersensitivity reactions

Hypersensitivity reactions as well as infusion-related reactions have been reported with anti-PD-L1 and anti-PD-1 therapy (Brahmer et al 2012). As with the administration of any foreign protein and/or other biologic agents, reactions following the infusion of mAbs can be caused by various mechanisms, including acute anaphylactic (IgE-mediated) and anaphylactoid reactions against the mAbs and serum sickness. Acute allergic reactions may occur, may be

severe, and may result in death. Acute allergic reactions may include hypotension, dyspnea, cyanosis, respiratory failure, urticaria, pruritus, angioedema, hypotonia, arthralgia, bronchospasm, wheeze, cough, dizziness, fatigue, headache, hypertension, myalgia, vomiting, and unresponsiveness. Guidelines for the management of patients with hypersensitivity (including anaphylactic reaction) and infusion-related reactions are provided in Table 1.

Hepatic function abnormalities (hepatotoxicity)

Immune-mediated hepatic function abnormalities include transaminitis, hepatitis and hepatotoxicity of any grade on concurrent tests. Concurrent findings are those that derive from a single blood draw or from separate blood draws taken within 8 days of each other. Follow-up investigations and inquiries will be initiated promptly by the investigational site to determine whether the findings are reproducible and/or whether there is objective evidence that clearly supports causation by a disease (eg, cholelithiasis and bile duct obstruction with distended gallbladder) or an agent other than the IP. Guidelines for management of patients with hepatic function abnormality are provided in Appendix 1.

Hy's Law

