			
methylprednisolone 2 to 4 mg/kg/day or equivalent, promptly start further immunosuppressives (eg infliximab at 5 mg/kg once every 2 weeks). Caution: Ensure GI consult to rule out bowel perforation and refer to infliximab label for general guidance before using infliximab.
 
 – Once the patient is improving, gradually taper steroids over ≥28 days and consider prophylactic antibiotics, antifungals, and anti-PCP treatment (refer to current NCCN guidelines for treatment of cancer-related infections [Category 2B recommendation]).^a
Hepatitis (elevated LFTs) Infliximab should not be used for management of immune-related hepatitis.	Any Grade	General Guidance	
For Any Grade:
 
 – Monitor and evaluate liver function test: AST, ALT, ALP, and TB. – Evaluate for alternative etiologies (eg, viral hepatitis, disease progression, concomitant medications).
	Grade 1 AST or ALT > to 3 × ULN and/or TB > to 1.5 × ULN)	No dose modifications. 
 • If it worsens, then treat as Grade 2 event. 	
For Grade 1:
 
 – Continue LFT monitoring per protocol.
	Grade 2 (AST or ALT > 3 to 5 × ULN and/or TB > 1.5 to 3.0 × ULN)	Hold study drug/study regimen dose until Grade 2 resolution to Grade ≤1. 
 • If toxicity worsens, then treat as Grade 3 or Grade 4. • If toxicity improves to Grade ≤1 or baseline, resume study drug/study regimen after completion of steroid taper. 	
For Grade 2:
 
 – Regular and frequent checking of LFTs (eg, every 1 to 2 days) until elevations of these are improving or resolved. – If no resolution to Grade ≤1 in 1 to 2 days, discuss with study physician. – If event is persistent (>3 to 5 days) or worsens, promptly start prednisone 1 to 2 mg/kg/day PO or IV equivalent. – If still no improvement within 3 to 5 days despite 1 to 2 mg/kg/day of prednisone PO

Specific Immune-mediated Reactions

Adverse Events	Severity Grade of the Event (NCI CTCAE version 4.03)	Dose Modifications	Toxicity Management

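### For an unexplained Grade 1 liver abnormality, Section 10.3.3.2 requires dosing to be interrupted, while the Appendix 1 hepatitis table calls for no dose change

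*Combined protocol and SAP*

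**What the plan says.** Section 10.3.3.2 applies to "Hepatic function abnormality (as defined in Section 10.1.3.) in a study subject, with or without associated clinical manifestations". It does two things. It sets a 24-hour reporting duty to the sponsor and the drug supplier, unless a definitive cause unrelated to study drug has been confirmed. It then gives a dosing instruction in two branches. Where an unrelated cause has been established, continuing is left to the investigator's judgment. Where it has not: "If no definitive underlying diagnosis for the abnormality is established, dosing of the study subject must be interrupted immediately".

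The definition it borrows is in Section 10.1.3: "Immune-mediated hepatic function abnormalities include transaminitis, hepatitis and hepatotoxicity of any grade on concurrent tests". Tests count as concurrent if they come from one blood draw or from draws within 8 days of each other. The same paragraph ends: "Guidelines for management of patients with hepatic function abnormality are provided in Appendix 1". Section 6.5.1 also refers dose modification to Appendix 1.

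In the Appendix 1 hepatitis table, the Grade 1 row is labelled "Grade 1 AST or ALT > to 3 × ULN and/or TB > to 1.5 × ULN". Its dosing entry is "No dose modifications", with escalation to the Grade 2 row if the values worsen, and its management entry is "Continue LFT monitoring per protocol". Holding of study drug begins at Grade 2.

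**The concern.** An investigator looking at an unexplained Grade 1 rise finds a mandatory interruption in one place and an instruction to leave dosing unchanged in the other. No sentence ranks the two. Exposure to durvalumab and tremelimumab would then depend on which page was consulted, in a trial whose primary endpoint is safety and tolerability.

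The situation is foreseeable. The schedule of assessments puts serum chemistry at cycle 1 weeks 1 and 3 and at later cycles, and its footnote requires safety bloods to be reviewed before each infusion. The two rules therefore meet at a dosing decision. Inclusion criterion 12 also lets patients enter with liver values already above normal, and Section 10.3.3.2 does not mention baseline.

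**Working it through.** The plan states no figure on this point, so the check is a comparison of the texts.

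**Step 1: do both rules cover the same result?** Section 10.3.3.2 imports the Section 10.1.3 definition, which has no lower grade limit but is qualified as immune-mediated and on concurrent tests. The introduction to Appendix 1 treats any event without a clear alternative cause as potentially immune related. An unexplained Grade 1 rise on concurrent tests can therefore fall under both.

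**Step 2: the dosing actions side by side.** The lower limit of the Grade 1 band is missing from the text available; I take it to be the ULN.

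| Unexplained result | Section 10.3.3.2 | Appendix 1, hepatitis table |
|---|---|---|
| Grade 1: AST/ALT to 3 x ULN and/or bilirubin to 1.5 x ULN | Interrupt at once | No change; keep monitoring |
| Grade 2: AST/ALT above 3 to 5 x ULN and/or bilirubin above 1.5 to 3 x ULN | Interrupt at once | Hold |
| Grade 3 | Interrupt at once | Hold or discontinue, by level and recovery |
| Grade 4 | Interrupt at once | Discontinue permanently |

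Only the first row conflicts.

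**Step 3: would another Appendix 1 table remove the conflict?** No. The general immune-related table and the non-immune table also give no dose modification at Grade 1.

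**Step 4: can a patient enter inside the band?** Inclusion criterion 12 allows AST/ALT up to 2.5 x ULN without liver metastases. Since 2.5 is below 3, values above ULN and up to 2.5 x ULN are both eligible and Grade 1. The Appendix 1 hepatitis table uses return to Grade 1 or baseline as a resumption criterion after higher grades; Section 10.3.3.2 has no counterpart.

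**Step 5: is there a restart rule?** Section 10.3.3.2 gives none. Appendix 1 allows resumption once a higher-grade event has come down to Grade 1 or less. A Grade 1 event meets that from the outset, so it cannot sensibly end an interruption that began at Grade 1.

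**Step 6: could this bear on the run-in?** Section 6.4 lists "Prolonged delay (>2 weeks) in initiating cycle 2 due to treatment-related toxicity". Cycle 2 is due on day 1 + 28 = 29, so a delay of more than 14 days is complete only after day 29 + 14 = 43. That is beyond the 28-day evaluation period in Section 6.4 but within the 8 weeks (day 56) used for the run-in in the synopsis.

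**The case against.** The strongest reply is that these are not two orders of equal force. Section 6.5.1 presents its dose adjustments as guidance that may be applied and describes Appendix 1 as recommendations, whereas Section 10.3.3.2 is mandatory. That softens the clash but does not settle it. If the mandatory sentence prevails, the Grade 1 row would apply only to explained cases, and the table does not say so. If the table prevails, the mandatory sentence is wrong at Grade 1.

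The definition is also narrower than a bare reference to any grade suggests. It requires an immune-mediated abnormality on concurrent tests, and Section 10.1.3 asks the site to check whether the finding is reproducible. An isolated mild rise may not qualify, and a value present before the first dose is not obviously immune-mediated. This stands as a limit on how often the conflict arises. It also shows that the handling of an abnormal baseline needs stating. Because there is one center, divergence between investigators is likely to be smaller than in a multicenter trial.

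Two stronger readings are tempting and are not supported:

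- A reader might infer that a Grade 1 laboratory value can by itself supply a DLT, and so help move the remaining 14 patients to the modified schedule. Section 6.4 opens with Grade 3 or higher and sets its own liver threshold (transaminases above 8 x ULN or bilirubin above 5 x ULN). The delay item requires treatment-related toxicity, which an undiagnosed abnormality does not establish. Laboratory findings must be confirmed by repeat testing before designation as a DLT in the absence of a clinically significant abnormality. The delay completes outside the 28-day period, and two DLTs are needed to change the schedule.
- A reader might infer that patients with liver metastases, admitted at up to 5 x ULN, are caught as well. Values above 3 x ULN are Grade 2, where Appendix 1 also holds. A rise explained by metastases falls under the branch of Section 10.3.3.2 that leaves dosing to the investigator.

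**Conclusion.** The contradiction holds for one defined case: an unexplained, immune-mediated Grade 1 hepatic abnormality on concurrent tests. There Section 10.3.3.2 requires interruption and the Appendix 1 hepatitis table, to which the protocol itself refers for management, makes no dose change. From Grade 2 upward both passages hold or discontinue.

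The conflict spans the whole Grade 1 band, and part of that band is open to patients at entry. Its frequency cannot be given, because the documents report no rate of unexplained Grade 1 liver abnormalities. The conclusion rests on the wording alone and on reading the band as starting at the ULN.

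Any effect on the run-in is secondary. A prolonged interruption could bear on the cycle 2 delay item only if the abnormality is attributed to treatment and the 8-week window, not the 28-day one, applies.

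**What to change.** Reconcile the dosing instruction in Section 10.3.3.2 with the Appendix 1 hepatitis table, so that one grade-specific rule covers both interruption and restart. State in the same place how the rule applies to a patient enrolled with an abnormal baseline value. Separate this from the 24-hour reporting duty, which can remain any-grade without carrying a dosing consequence. Which rule is clinically right is for the sponsor to decide.

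Optionally, clarify in Section 6.4 whether a cycle 2 delay arising only from such an interruption is meant to count, once the DLT window itself is settled.

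The cost is a wording amendment to Section 10.3.3.2 with a matching cross-reference in Appendix 1. It needs no extra tests, visits or patients.
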